1.3 Schema

Week 1 through Week 4	Enrollment and Training

 • Total n=5 anesthesiologists, 10 CRNAs/anesthesia residents/fellows (user subjects) • Identify user subjects - anesthesiologists and their teams of CRNAs, anesthesia residents and fellows performing planned airway procedures under general anesthesia. • Obtain informed consent from willing user subjects and complete intake questionnaire • Document and record contact information for user subjects • Review user manual and device use. 	
Week 1 through Week 6	Device Use and Assessment

 • Protective device use and aerosol evacuation during airway procedures under general anesthesia on COVID-19-negative patients • Patients (patient subjects) of anesthesiologists participating as user subjects in the study will be recruited on the day of procedure. • Patient subjects will be randomized to intubation with or without the biocontainment device. • Goal of obtaining data from 150 airway procedures under general anesthesia in the device (100 with the device and 50 without the device). • Patient subject Data and data from record of airway procedure will be recorded after each device use • Quality Use Survey, including documentation of any AEs will be completed by user subjects at the end of each day • Patient experience questionnaire completed by patient subject randomized to device use within 1 week after procedure 	

- AE event summary reconciliation and review performed weekly
- Feedback on quality use data use and user suggestions given to engineering team every two weeks
- Interval assessment by the medical director of intubation data from medical record, quality use survey data, including summary of AEs, and preliminary analysis of post-training questionnaire/intake data every two weeks

Week 4 through Week 12	Device Use and Assessment, Final Data Analysis
	
• Continued use and assessment of biocontainment device if needed to meet enrollment numbers• Final Feedback on device use and user suggestions given to engineering team• Final assessment of survey data and device utilization

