4 STUDY PLAN

4.1 Study Design

This is a multi-site (HUP, PPMC), unblinded, randomized, observational study performed in a controlled environment in the operating room. The hypothesis is that rapid sequence intubation or other urgent airway procedures performed with the biocontainment device will be safe and can be performed in an equivalent manner to urgent airway procedures without the biocontainment device. Methods to minimize bias include randomizing patients to intubation with or without the biocontainment device. Stratification of results will be performed as described in [Section 9.4.7](#) below.

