6.3 Measures to Minimize Bias: Randomization and Blinding

Randomization will be done to assign patients to intubation with or without the biocontainment device in a 2:1 fashion. This will allow for analysis of patient-related intubation factors as well as user-related intubation factors as part of the feasibility analysis. Blinding is not possible with this study as all users and patients will be aware of the presence of the device intervention. To help minimize bias in the data analysis, results of all data analysis will be assessed by a neutral, third-party with expertise in statistical analysis.

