Airway procedure and patient data collection: Patient data and data from the anesthesia data record will be collected by PIs or their qualified designee post-airway procedure. As a result of social distancing and minimizing personnel due to COVID-19, it may not be possible to have a member of the research team present to observe and record data from each procedure. The airway procedures will be recorded using a GoPro camera placed in a fixed position. Data from the memory card will be transferred to an institutionally secured and managed network drive. Device use data will be collected from the videos by the PI or qualified designee. This data will include length of time to setup the device, length of time to perform the airway procedure, length of time to remove the device, number of times hand ports were used per procedure, and positioning of the torso drape. Patient data collected from the medical record will include patient demographics, contact information (phone and email), age, gender, race, co-morbid conditions (i.e. cardiac disease, lung disease, diabetes, BMI), smoking status. Airway procedure-related data that will also be collected will include BMI, hyomental distance, Mallampati score, type of airway procedure performed, number of attempts to perform the airway procedure, devices used for airway procedure, use of mask ventilation, anesthesia sequence used, and experience level of person performing the airway procedure.

Quality Use Survey and Safety Data Collection: As part of the study, user subjects will complete a Quality Use Survey after each day using the device. The results of the survey will be transferred from hard copies or REDCap to electronic format in CTMS for storage. This survey will collect user information on device functionality, perceived benefit of device use, healthcare burden associated with the device and safety data associated with device use. Safety data collected will include: 1) injury to the patient subject (patient in ABCD) or user subject (healthcare provider), 2) healthcare provider perceived patient subject anxiety or claustrophobia, 3) difficulty performing intubation with or without requiring removal of the device, 4) observed device defects or failures (i.e. broken strap, crack in plexiglass, break in hand ports).

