Patient Subject Experience Survey: The patient subject's randomized to device use will be asked in the recovery room post-procedure or receive a phone call or email with REDCap survey link from a qualified study coordinator to answer a short patient experience survey where the data will be collected in REDCap and subsequently transcribed into CTMS. Data collected will include: 1) overall comfort in the device, 2) sensation of increased anxiety, 3) sensation of claustrophobia, 4) perceived safety in the device, 5) any difficulties seeing or hearing while in the device, 6) any additional comments or suggestions regarding the experience in the device. All data will be collected on a Likert scale and stored in CTMS.

Patient subjects' medical records medical will be accessed as part of the study. Personal and medical data collected as part of the study will be stored in a de-identified fashion on an institutionally secured and managed network drive and/or computer.

As part of this study, user subjects' medical records will NOT be accessed. Personal data including age, and gender, will be collected as part of the initial data collection instrument and stored in de-identified fashion on an institutionally secured and managed network drive and/or computer.

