8.3 Adverse Events and Serious Adverse Events

8.3.1 Definitions

8.3.1.1 Adverse Event/Adverse Device Effect

An **adverse event** (AE) or adverse device effect (ADE) is any untoward medical occurrence (sign, symptom, or experience) that develops or worsens in severity associated with the use of the biocontainment device, whether or not considered intervention related. Intercurrent illnesses or injuries should be regarded as adverse events. A pre-existing condition should be recorded as an adverse event if the frequency, intensity or the character of the condition changes. Abnormal results of the intervention are considered to be adverse events if the abnormality:

- results in study withdrawal
- is associated with a serious adverse event
- is associated with clinical signs or symptoms
- leads to additional treatment or to further resource utilization (diagnostic tests/procedures)
- is considered by the investigator to be of clinical significance

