8.3.3 Time Period and Frequency for Event Assessment and Follow-Up

Safety will be assessed by monitoring and recording potential adverse effects using the quality use survey and the patient survey questionnaire as defined in [Section 1.3](#). Participants will be monitored by these questionnaires. Any adverse events/ADEs are captured and shared with study PIs and the Sponsor. AEs and SAEs will be assessed for daily and completeness of surveys (data integrity) will be assessed weekly.

The investigator will seek information on adverse events by non-directive questioning. Adverse events may also be detected when they are volunteered by the clinician utilizing the device. Information on all adverse events will be recorded in the source documentation. To the extent possible, adverse events will be recorded as a diagnosis and symptoms used to make the diagnosis recorded within the diagnosis event.

As much as possible, each adverse event or follow-up information will be evaluated to determine:

1. Severity grade (as described in [Section 8.3.2.1](#) above)
2. Duration (start and end dates)
3. Relationship to the study treatment or process – (As described in [Section 8.3.2.2](#) above)
4. Expectedness to study treatment or process – [Unexpected – if the event severity and/or frequency is not described in the investigator brochure (if applicable) or protocol].
5. Action taken with respect to investigational device or process (none, permanently discontinued, unknown, not applicable)
6. Whether the event is serious

Once an adverse event is detected, it should be followed until its resolution or until it is judged to be permanent, and assessment should be made weekly (or more frequently, if necessary) of any changes in severity, the suspected relationship to the study treatment, the interventions required to treat it, and the outcome.

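### Solicited safety data are collected unequally by arm, so user-reported difficulty, minor injury and anxiety cannot be compared fairly between device and control procedures

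*Combined protocol and SAP*

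**What the plan says.** The trial has a randomised control. Section 6.3 states: "Randomization will be done to assign patients to intubation with or without the biocontainment device in a 2:1 fashion". The Schema (1.3) gives the numbers: "Goal of obtaining data from 150 airway procedures under general anesthesia in the device (100 with the device and 50 without the device". Section 4.1 hypothesises that urgent airway procedures with the device "will be safe and can be performed in an equivalent manner to urgent airway procedures without the biocontainment device".

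Primary endpoint 2 is the number of AEs and adverse device effects (ADEs) over time. Section 8.3.3 names the sources: "Safety will be assessed by monitoring and recording potential adverse effects using the quality use survey and the patient survey questionnaire", and refers to the Schema for their definition.

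- **Patient survey.** The Schema reads: "Patient experience questionnaire completed by patient subject randomized to device use within 1 week after procedure". Section 8.1 has the same restriction: "The patient subject's randomized to device use will be asked in the recovery room post-procedure".
- **Quality Use Survey.** Section 8.1 says "user subjects will complete a Quality Use Survey after each day using the device". Section 8.2 has device-utilisation questionnaires completed after each use of the device. The Schema has users complete the survey, including any AEs, at the end of each day and does not mention device use in that line.
- **AE definition.** Section 8.3.1.1 covers an untoward occurrence "that develops or worsens in severity associated with the use of the biocontainment device".
- **Analysis.** Section 9.4.2 plans total counts and a logistic regression on user experience, procedure type and patient factors. Randomised arm is not among the factors named.

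**The concern.** Several of the expected events in 8.3.2.3 (minor injury, patient anxiety, difficulty with intubation) also occur in ordinary airway management. A count from device procedures alone mixes that background with any effect of the device. The randomised controls could supply the background, but only if the same questions are asked about them.

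As written, the device arm gets a checklist and the control arm mostly does not. If events were tabulated by arm, the device would look worse simply because more was asked about it. If they were not tabulated by arm, background events would rest on case-by-case causality grading. Either way, the 50 controls would add little to one of the two primary objectives. The loss is hard to repair later, because user and patient impressions are not recorded elsewhere and 10.1.4 and 10.1.8.1 have the videos deleted within 14 days.

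**Working it through.** **1. Planned numbers.** A 2:1 split of 150 gives 150 × 2/3 = 100 device and 150 × 1/3 = 50 control procedures, which agrees with the Schema. The minimum of 97 in 9.2 is a single-proportion precision figure: 1.96² × 0.25 / 0.10² = 96.04, rounded up. It was not derived for a between-arm comparison of events.

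**2. What reaches a control procedure.**

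| Route | Section | Covers controls? |
|---|---|---|
| Patient survey | 1.3, 8.1 | No, device arm only |
| Quality Use Survey | 1.3 | Possibly, completed daily |
| Quality Use Survey | 8.1 | Only if a control case falls on a device-use day |
| Device-use questionnaire | 8.2 | No, after each device use |
| Survey safety items | 8.1 | Injury item identifies the patient as the one in the device; difficulty item refers to its removal |
| Expected difficulty event | 8.3.2.3 | No, defined with the device in place |
| Open questioning | 8.3.3 | Yes |
| Volunteered reports | 8.3.3 | Described for the clinician using the device |
| AE reporting from consent; all SAEs | 8.3.4 | Yes, but the AE definition is tied to the device |
| Attempts, mask ventilation | 8.1 | Yes, no arm restriction |
| Procedure time | 9.4.2 | Yes, with and without the device |

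The objective measures are symmetric. The solicited ones are not.

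**3. Size of the bias.** Let p be the true event rate in both arms, and let s_D and s_C be the fractions of events captured. The expected observed difference is p × (s_D − s_C). The documents give neither rates nor capture fractions. With p = 10% assumed and s_D = 1, the spurious excess runs from 0 points (s_C = 1) to 10 points (s_C = 0).

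**4. What symmetric capture would show (assumed counts).** Ten events in 100 device procedures is 10%, exact 95% CI 4.9% to 17.6%. The Newcombe interval for a difference d is d − √[(p₁ − l₁)² + (u₂ − p₂)²] to d + √[(u₁ − p₁)² + (p₂ − l₂)²], where l and u are Wilson limits. For 10/100 these are 5.5% and 17.4%.

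- Against 3/50 (6%; Wilson 2.1% to 16.2%): d = 4 points, 95% CI −7.2 to +12.4.
- Against 1/50 (2%; Wilson 0.4% to 10.5%): d = 8 points, 95% CI −1.6 to +15.6.

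**5. Precision and power with 50 and 100.** The 95% half-width at a common rate p is 1.96 × √[p(1 − p)(1/50 + 1/100)]: 7.4 points at 5%, 10.2 at 10% and 13.6 at 20%.

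Power, two-sided 5%, is Φ[(|p₁ − p₀| − 1.96 × SE₀)/SE₁], with SE₀ pooled and SE₁ unpooled. For 30% versus 10%, the pooled rate is (50 × 0.10 + 100 × 0.30)/150 = 0.233, SE₀ = 0.0733 and SE₁ = 0.0624. This gives Φ(0.90) = 0.82 (exact Fisher 0.81). Other assumed pairs, by the same formula:

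- 15% versus 5%: 0.43 by the formula, 0.40 by Fisher.
- 20% versus 10%: 0.33 and 0.31.
- 20% versus 5%: 0.72 and 0.72.
- 25% versus 5%: 0.90 and 0.91.

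**The case against.** The strongest reply has four parts.

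- **The survey may cover controls.** Section 8.3.3 defers to the Schema, where the Quality Use Survey is daily with no stated device restriction. Even under the 8.1 trigger, a form-day may include control cases from the same user. This stands as far as it goes: the documents are inconsistent on the trigger and do not prove an absence of control data. It does not help the patient survey, and a daily form would still carry device-framed items.
- **Difficulty is measured another way.** Attempts, mask ventilation and time are available in both arms. This stands in full for objective difficulty. These measures do not capture injury, anxiety or the user's own report of difficulty.
- **The objective is not worded as a comparison.** Primary objective 2 concerns events associated with device use, 9.1 expects them to be few and declining, and the equivalence statement in 9.1 is about time only. This is fair. The hypothesis in 4.1 and the randomised control nevertheless make a comparison the natural reading.
- **Events are graded for causality, and power is low.** Section 8.3.2.2 allows a grade of unrelated, so events are not attributed to the device automatically. The same section also lets timing alone support a probable or possible grade. The factors listed for the regression follow the word including, so the missing arm term is weak evidence by itself. The two intervals in step 4 overlap heavily and both include zero. Low power is a reason to estimate rather than test; it does not justify unequal questioning.

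**Conclusion.** The concern holds as one of unequal ascertainment. Solicited safety items are collected mainly or only for device procedures, so user-reported difficulty, minor injury and anxiety cannot be compared between arms without bias against the device. The size of that bias cannot be computed from the documents; with an assumed true rate of 10% and full capture in the device arm, it lies between 0 and 10 points.

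A reader might infer that the controls yield no background information at all, or that device safety cannot be addressed comparatively in any respect. The documents do not support that. Objective airway measures are collected in both arms, control AEs and SAEs can be reported, one of the three survey triggers is not limited to device use, and the safety objective is worded in terms of device-associated events.

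This should be fixed before enrolment because the fix is cheap and the lost information is hard to recover. It does not affect the procedure-time endpoint or invalidate the trial.

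**What to change.** 1. **Sections 1.3, 8.1 and 8.2:** reconcile the survey trigger to a single one, every randomised procedure in both arms.
2. **Sections 8.1 and 8.3.3:** have the user complete the same arm-neutral items each time: injury to patient or provider, perceived patient anxiety, and difficulty performing the airway procedure. Keep device-only items (device removal, defects) for the device arm.
3. **Section 8.3.1.1:** define an AE without reference to arm, as an untoward occurrence during or after the study airway procedure, and reserve ADE for device-related events. Align the expected difficulty event in 8.3.2.3.
4. **Section 9.4.2:** report each shared event, and the number of attempts, by arm with the difference and 95% CI. State that this is estimation rather than a powered test, since 50 versus 100 reaches about 80% power only for large differences such as 30% versus 10% (assumed rates).

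The cost is a short amendment and one brief form for about 50 control procedures, completed by users already enrolled. It needs no extra patients or procedures; the downside is a little more survey burden.

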8.3.4 Adverse Event Reporting

Reporting Period

Adverse events will be reported from the time of informed consent until study completion.

Investigator Reporting: Notifying the Study Sponsor and via the Medical Director.

Every SAE/UADE, regardless of suspected causality (e.g., relationship to study product(s)) must be reported to the medical director and sponsor within 24 hours of learning of its occurrence.

Recurrent episodes, complications, or progression of the initial SAE must be reported to the Sponsor as a follow-up to the original episode within 24 hours of the investigator receiving the follow-up information. A SAE/UADE considered completely unrelated to a previously reported one should be reported separately as a new event.

Send the SAE report to the Medical Director.

New information regarding the SAE or UADE will be reported as it becomes available and in the same manner that the initial SAE (i.e., MedWatch form). The investigator must follow the event to resolution or until the event is deemed and documented irreversible, whichever is longer.

Investigator Reporting: Local Reporting Requirements

The investigator will report AEs/ADEs and SAEs/UADES to the IRB/EC of record and other local regulatory groups per the local requirements. Additional reporting/requirements include: failure to obtain ICF, device recall/repair/disposal, change in risk determination, or FDA or IRB withdrawal of the study.

8.3.5 *Serious Adverse Event Reporting*

The study PI will immediately report to the sponsor any serious adverse event or UADE, whether or not considered biocontainment device related, including those listed in the protocol and must include an assessment of whether there is a reasonable possibility that the biocontainment device caused the event.

New information regarding the SAE or UADE will be reported as it becomes available and in the same manner that the initial SAE/UADE (i.e. SAE form). All serious adverse events (SAEs) and UADEs will be followed until satisfactory resolution or until the site investigator deems the event to be chronic or the participant is stable. Other supporting documentation of the event may be requested by the study sponsor and should be provided as soon as possible.

The SAE and UADE reports along with the PI's assessment are to be sent to the Sponsor medical director within 24 hours. AEs and ADEs are to be entered into CTMS weekly, no later than 7 calendar days after each event. The sponsor and medical director will review these events no less than weekly.

The study investigator shall complete an Unanticipated Adverse Device Effect Form and submit to the study sponsor and medical director and to the reviewing Institutional Review Board (IRB) per IRB policy. The study sponsor is responsible for conducting an evaluation of an SAE/UADE and shall report the results of such evaluation to all reviewing IRBs and FDA as applicable.

8.3.6 *Reporting Events to Participants*

SAEs and UADEs will be reported to study user subjects within 24-hours of assessment completion by the Study sponsor and medical director.

8.3.7 *Events of Special Interest*

Not Applicable.

8.3.8 *Reporting of Pregnancy*

Potential User-Subjects who are pregnant are excluded from this trial due to any potential risks associated with lifting the device. If a study participant becomes pregnant, they should inform the PI team. They do not need to disclose pregnancy status as the reason for study withdrawal.

9 STATISTICAL CONSIDERATIONS

9.1 *Statistical Hypotheses*

We hypothesize that the biocontainment device will be a safe and effective option for performing airway procedures in patients while also providing additional protection during an aerosol generating procedure.

Primary Efficacy Endpoints:

1. We hypothesize that the time to perform an airway procedure with the biocontainment device will be equivalent to time for airway procedure without the biocontainment device. Alternatively, there will be prolonged airway procedures times with the device. This endpoint will be analyzed every two weeks.
2. We anticipate that the number of AEs or ADEs will be low and will also decrease over time. This endpoint will be analyzed on a weekly basis.

Secondary Efficacy Endpoints:

1. We hypothesize that the median Likert ratings for User subject device comfort will be weighted toward “strongly agree”. Alternatively, we will see ratings favoring “neutral” or “disagree” for user subject device comfort.
2. We hypothesize that the median Likert ratings for User subject additional healthcare burden comfort will be weighted toward “strongly disagree”. Alternatively, we will see ratings favoring “neutral” or “agree” on increased healthcare burden.
3. The median Likert ratings for the Patient Experience survey will be weighted toward minimal patient discomfort or anxiety. Alternatively, we will see ratings favoring increased patient discomfort or anxiety inside the device.
3. We anticipate that the median Likert ratings of the patient experience post-survey will indicate overall good user comfort and low levels of anxiety or claustrophobia in the device.

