1 STUDY SUMMARY

1.1 Synopsis

Title: Aerosol Biocontainment Device (ABCD) with Aerosol Clearance for Aerosol Generating Procedures

Short Title: Aerosol BioContainment Device (ABCD)

Study Description: The primary goal of this study is to assess use of a biocontainment device for planned airway procedures under general anesthesia. This will serve as a platform for using this device as a novel biocontainment and aerosol evacuation system as part of rapid sequence intubation protocols for COVID-19 patients. We hypothesize that airway procedures with the aerosol biocontainment device will be safe and effective with airway procedure times approaching times for airway procedures without the device.

Objectives: The primary objectives of this study are: 1) Assess changes in airway procedure time with and without the biocontainment device as a function of repeated utilization and as a function of patient-associated airway factors (i.e. Mallampati score, hyomental distance, neck mobility, BMI) and user-associated airway factors (i.e. experience of user, airway device used, induction sequence) 2) Assess adverse events, adverse device events associated with biocontainment device use.

Secondary objectives include: 1) Assess the subject's comfort with using the biocontainment device. 2) Assess for additional healthcare and cognitive burden imposed by the device. 3) Survey of patient's post-procedure on experience being inside the device. Exploratory objectives include gathering specific feedback regarding possible design modifications for further iterations and design improvements with the engineering team.

Primary Endpoint: The primary endpoints of this study are:
1. Measuring the time for performing an airway procedure with the biocontainment device when accounting for patient and user-specific factors.
2. Quantifying the number of AEs or ADEs over time to assess device safety.

Secondary Endpoints: The secondary endpoints include:
1. Median Likert ratings from device use survey questions that assess user subject device comfort.
2. Median Likert ratings from device use survey questions that assess user subject healthcare burden with the device.
3. Median Likert rating of the patient questionnaire results to assess patient experience in the device.

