The Sponsor medical director is responsible for determining whether an adverse event (AE) or ADE is expected or unexpected. An AE or ADE will be considered unexpected if the nature, severity, or frequency of the event is not consistent with the risk information listed in the Investigational Plan.

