9.4.2 Analysis of the Primary Efficacy Endpoint(s)

Primary Endpoints:

1. Assessment of time to complete an airway procedure with or without the biocontainment device. The time is measured as a single quantitative measure at the end of the procedure. The initial starting time (T0) is defined as “time the mask is removed from the patient just prior to initiation of the airway procedure”. End time (T1) is defined as the time that the airway procedure is completed with a secure airway defined as the

time the airway device is secured to the airway circuit. Data will be presented as median amount of time for a given procedure with or without the biocontainment device and statistical significance will be determined by analysis of variance (ANOVA). Additionally, a multiple regression model will be created using covariates of subject user experience, number of prior uses with the device, and patient specific factors (co-morbid conditions, BMI, Mallampati score). This will help determine the critical factors associated with time to use the device.

2. The total number of AEs and ADEs will be presented. This will be broken down by specific AE or ADE. Logistic regression will be used to assess possible contributing factors to AEs or ADEs including subject user experience, airway procedure performed, patient-specific factors (BMI, co-morbid conditions, Mallampati score). We anticipate a low number of AEs/ADEs and as such, statistically rigorous regression analyses may be limited by a low overall number of events.

Statistical analyses will be performed on all data points, however, a sub-analysis will be performed on participants without any missing data points.

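### The primary safety endpoint is reported as event counts with no interval or reference for any event risk, so the planned output does not show which risks 100 device uses can exclude

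*Combined protocol and SAP*

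**What the plan says.** The Synopsis (1.1) gives the second primary endpoint as "Quantifying the number of AEs or ADEs over time to assess device safety". Section 3 adds breakdowns by time and by user. The only statistical form of the safety hypothesis is in Section 9.1: "We anticipate that the number of AEs or ADEs will be low and will also decrease over time".

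The analysis is in Section 9.4.2: "The total number of AEs and ADEs will be presented. This will be broken down by specific AE or ADE". It continues: "Logistic regression will be used to assess possible contributing factors to AEs or ADEs including subject user experience, airway procedure performed, patient-specific factors". Device versus no device is not among the factors listed, and the same section warns that few events may limit the regression. Section 9.4.4 (Safety Analyses) refers back to 9.4.2 and adds no method.

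The Schema (1.3) sets the arm sizes at "100 with the device and 50 without the device", matching the 2:1 allocation in Section 6.3. The analysis set in Section 9.3 is per-protocol. Section 9.4.1 names a 95% confidence interval, but for judging improvement in outcomes, with COVID-19 cases among participants as its example. Section 8.3.2.3 lists the expected events and says how unexpectedness is judged: "An AE or ADE will be considered unexpected if the nature, severity, or frequency of the event is not consistent with the risk information".

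**The concern.** Safety is half of the primary hypothesis, yet the plan attaches no number to a low count. A total and a list by type describe what happened in this sample. They do not tell a reader what true risk is compatible with it. For common events such as anxiety the gap is modest, because the count itself is informative. For rare, serious events a count of zero or one is the likely result under a wide range of true risks, and without an interval the reader cannot see that range.

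The stakes lie in what comes next. The Synopsis presents the study as a platform for using the device in rapid sequence intubation of COVID-19 patients. Anyone taking that step needs to know which risks 100 planned procedures have ruled out and which they have not.

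**Working it through.** **Inputs.** 100 device uses and 50 controls (Schema 1.3; 2:1 in 6.3). 95% confidence, the level used in 9.2 and 9.4.1. A 10–15% loss rate (9.2). 15 users in the Schema (5 anesthesiologists plus 10 others), 15 to 20 in Section 5.5.

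**The plan's own figure.** Section 9.2 reaches 97 procedures from a precision formula for one proportion: 1.96² × 0.5 × 0.5 / 0.1² = 3.8416 × 0.25 / 0.01 = 96.04, rounded up to 97. This reproduces. (The formula as printed, with 0.5² × (1 − 0.5²), would give 72.03; the next printed line uses 0.25, which is the standard form.) The figure sets a margin of 10 percentage points at a proportion of 50%. It is not derived from any AE rate. The documents state no figure for the AE/ADE endpoint.

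**Upper limit when no event of a given type is seen.** The exact (Clopper–Pearson) limit solves (1 − p)ⁿ = α/2 for a two-sided interval, or α for a one-sided bound.
- Two-sided 95%, n = 100: 1 − 0.025^(1/100) = 3.62%. As a check, (1 − 0.036)^100 = 2.6%. The Wilson limit is 3.70%, so the choice of method matters little.
- One-sided 95%, n = 100: 1 − 0.05^(1/100) = 2.95%.
- Controls, two-sided, n = 50: 1 − 0.025^(1/50) = 7.11%.

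**Chance of seeing no event in 100 uses.** True risk 1%: 0.99^100 = 36.6%. True risk 2%: 0.98^100 = 13.3%.

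**If a few events are seen in 100 uses** (exact two-sided 95% interval):

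| Events | Interval |
|---|---|
| 1 | 0.03% to 5.4% |
| 2 | 0.2% to 7.0% |
| 3 | 0.6% to 8.5% |
| 5 | 1.6% to 11.3% |

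**If the denominator shrinks.** Section 9.2 applies its 10–15% between 175 screened and 150 enrolled, so applying it to the 100 device uses is an assumption about what the per-protocol set might lose. At 10%, n = 90 and the zero-event limit is 1 − 0.025^(1/90) = 4.02%. At 15%, n = 85 and it is 1 − 0.025^(1/85) = 4.25%.

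**Independence.** These limits treat the 100 uses as independent. Counting one user per use, the average is 100/20 = 5 to 100/15 = 6.7 uses per user. If risk differs between users or falls with practice, the binomial interval is likely to be too narrow. The documents give nothing from which to quantify this.

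**The case against.** Four parts of the case for the plan carry weight.

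First, a reader might infer that the device will be declared safe if the count is zero. No such rule exists. Section 9.1 states an anticipation, and Sections 2.2 and 4.2 describe a safety and feasibility study meant to refine protocols and labelling.

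Second, a device arm free of all events is improbable. Sections 2.2.2 and 8.3.2.3 list anxiety, claustrophobia and difficult intubation among the expected events, and the surveys in 8.1 ask about them. The 3.6% therefore applies to one rare event type, not to the arm's AE total.

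Third, more than a total is planned: breakdowns by type, time and user, and a regression. Oversight does not depend on a confidence interval either. There is weekly review by the sponsor and medical director (8.3.5), a pause on an upward trend (9.4.5), a condition on continuing (8.2) and grounds for termination (10.1.2). None of these carries a numerical rate, but an excess of events could still be acted on.

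Fourth, data are collected procedure by procedure from video and anesthesia records (8.1), so a reader with the counts and denominators could work out intervals. The gap is mainly one of reporting.

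The margin in 9.2 is also widest at 50%, so absolute precision at low rates is better than 10 points. What survives is that the plan commits to no proportion, interval or reference for any AE/ADE risk. The 50 controls do not supply the reference as written, because no AE comparison is specified and Section 8.3.1.1 defines AEs through use of the device.

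**Conclusion.** The concern holds as a gap in the analysis and reporting of a primary endpoint. For a single event type not seen in 100 device uses, the trial excludes risks above about 3.6% (two-sided) or 2.95% (one-sided), and about 4.0–4.3% two-sided if 10–15% of uses are lost. A true 1% risk would go unseen 37% of the time. These figures assume independent uses and, for the main figure, that all 100 device uses are counted. Closing the gap does not affect enrolment or conduct, but it changes what the trial can claim.

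Three stronger readings are not supported. One is that the plan contains no confidence interval at all: Section 9.4.1 names one in general terms, though not for AE/ADE risk. Another is that an excess of expected events could never be classed as unexpected because the risk sections use only words. Section 8.3.2.3 leaves that decision to the sponsor's medical director, and a very high frequency would plainly conflict with risks described as small or low; the criterion is vague, not inoperative. The third is that the plan is deficient for not giving an expected frequency for each event. The Synopsis says the device is new to healthcare settings, so such figures would be largely guesses.

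**What to change.** In Section 9.4.2, report for each event listed in 8.3.2.3 the number and proportion of device uses with at least one such event, with an exact 95% interval. Use all device uses as the denominator, not the per-protocol set, and note that uses are clustered within about 15 to 20 users, so the intervals may be too narrow. For events that can occur in both arms, such as difficult intubation, show the 50 controls alongside; this needs the event recorded the same way in both arms. The patient survey goes only to the device arm, so survey-reported anxiety and claustrophobia cannot be compared.

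In Section 9.1, state that 100 uses free of a given event exclude only risks above about 3.6% (two-sided 95%), and limit the safety conclusion to what the upper limits exclude.

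The cost is one table column and a few sentences. Because Section 8.1 has the user survey completed once per day of use, the form should tie each reported event to its procedure. The downside is a more modest safety claim.
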